7.3 Additional Efficacy Endpoints – Part II

- Assessment of pulmonary outcomes at 3, 6, 9 and 12 months corrected age
- Length of NICU Stay (LOS)
- Proportion of subjects with any respiratory resource utilization at 3, 6, 9 and 12 months corrected age
- Respiratory morbidity per quarter till 12 months corrected age
- Assessment of modified GMFS at 12 months corrected age

8 SAFETY ASSESSMENTS

Safety and tolerability will be assessed through the monitoring of oxygenation, bradycardia, nasal congestion/aspiration, and other adverse events (AEs) of interest to 40 weeks PMA or discharge. Tolerance of the AeroFact dosing administration and all doses of bolus surfactant will be assessed during and following dosing. Safety assessment frequency is shown in the Schedule of Assessments and Procedures.

8.1 General Safety Procedures

8.1.1 Ventilator/Respiratory Measurements

Serial measurements of respiratory support will be collected from the time of birth through 28 days of life, 35 to 37 Weeks PMA, 39 through 40 Weeks PMA and at the time of discharge from the NICU for all groups. If infants are discharged from the NICU prior to 36 and or 40 weeks, the study staff will collect applicable 36/40 week PMA information by telephone. Measurements include: Mode of support (CPAP, Continuous Mandatory Ventilation [CMV], High Frequency Oscillatory Ventilation [HFOV]/High Frequency Jet Ventilation [HFJV], NIMV/Bilevel Positive Airway Pressure [BiPAP], high flow nasal cannula (HFNC) or nasal cannula (NC) > 2 liters per min (L/min), NC \leq 2 L/min, or room air (RA), CPAP/PEEP, mean airway pressure (Paw), flow rate, FiO₂, SpO₂, and respiratory support status. A room air challenge (RAC) will be performed on those infants on nasal cannula support at 36 and 40 Weeks PMA. Duration of assisted ventilation and supplemental oxygen will also be collected. See Manual of Operations (MOP) for detailed instructions regarding the process for performing a RAC.

8.1.2 Weight Measurements

Weight (grams) will be obtained at the time of birth, discharge from NICU and 12 month corrected age assessment (Part II- by parent/guardian report). Head circumference and recumbent length will be collected at birth and discharge from the NICU.

8.1.3 Nasal Congestion

Prior to and during the AeroFact dosing period and bolus instillation of surfactant, the patency of the nasal prongs and blockage of nostrils with surfactant and/or secretions will be closely monitored and the severity of nasal congestion will be assessed every 15 minutes for the duration of dosing or a minimum of 2 hours. Document any suctioning done (none/oral/nasal/ETT) following AeroFact or bolus instillation of surfactant.

8.1.4 Surfactant Dosing Tolerance

Tolerance of surfactant dosing by AeroFact or bolus instillation will be assessed at 4 hours and 24 hours after the start of administration.

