Follow-Up Telephone Questionnaire ¹²								X

¹ Informed consent may be obtained prenatally² Blood gases (pH, PCO₂, PO₂, HCO₃-, base deficit) will be obtained prior to enrollment and intubation or in relationship to an SAE (if clinically obtained).³ Recumbent Length and Head Circumference at birth and discharge from NICU only⁴ AeroFact administered by nCPAP/nIMV or nCPAP/nIMV alone is to be initiated within 24 hours after birth. The anticipated duration of each AeroFact dosing is approximately approximately 2 hours.⁵ Re-dosing of AeroFact will be allowed if the RSS to maintain SpO₂ between 90 and 95% is 1.5 to 2.39 and at least two hrs. have elapsed since the start of the previous dose. If RSS is in range and FiO₂ >0.23, re-dosing will occur. If RSS is in range and FiO₂ is ≤0.23, re-dosing may occur at the discretion of the investigator. Up to 3 additional doses of AeroFact within 96 hrs. will be allowed.⁶ Oxygenation and respiratory parameters (FiO₂, SpO₂ [%], Positive-End Expiratory Pressure [PEEP]/CPAP [cm H₂O], Flow Rate [L/min], Mean Airway Pressure [Paw in cm H₂O], and Respiratory Support Status) will be obtained prior to dosing with AeroFact

delivery, every 15 minutes from the start of AeroFact dosing (T₀ to end of dose or a minimum of 2 hours). These parameters will be collected after the start of AeroFact administration or bolus instillation of surfactant for all groups.

⁷ Days 1-7 oxygen and resp. parameters will be obtained q 8 hrs., followed by daily from Days 8-28 and daily from 35 to 37 Wks. PMA and 39 through 40 Wks. PMA. Monitoring of O₂/resp parameters will occur at the same frequency for all groups.

⁸ Respiratory Support Status at 36 & 40 weeks PMA will be assessed by telephone if patient was discharged prior to that timepoint.

⁹ Nasal congestion/nasal aspiration will be assessed prior to and during each AeroFact dose or bolus instillation of surfactant for all groups.

¹⁰ Dosing tolerance completed at 4 and 24 hrs. after start of AeroFact administration or bolus instillation of surfactant for all groups.

¹¹ RAC will be performed if infant is on nasal cannula \leq 2 L/min and oxygen or nasal cannula $<$ 4 L/min in room air.

¹² Pulmonary outcomes will be assessed at 3, 6, 9 and 12 months corrected age and Neurologic Outcomes at 12 months corrected age. See Appendix II

TABLE OF CONTENTS

INVESTIGATOR'S SIGNATURE PAGE.....	3
1 CLINICAL PROTOCOL SYNOPSIS.....	4
TABLE OF CONTENTS	12

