2 BACKGROUND AND RATIONALE

2.1 Introduction

Aerogen Pharma is developing AeroFact, an investigational drug/device combination product consisting of lyophilized bovine-origin surfactant SF-RI 1 (sold in Europe since 1989 under the proprietary name AlveoFact®) administered following reconstitution to a 45 mg/ml suspension with semi-isotonic saline buffer using a proprietary breath-actuated vibrating mesh nebulizer with a nasal cannula interface.

Current surfactants used for prevention or treatment of Respiratory Distress Syndrome (RDS) in preterm infants are approved for delivery only as a liquid bolus instillation via an endotracheal tube (ETT) while intubated/cannulated. Intubation and cannulation with a tube into the trachea for surfactant administration are associated with adverse events (AEs) [1,2,3]. Access to surfactant therapy without invasive procedures that further exacerbate the condition is therefore a major unmet medical need in this vulnerable population. Reports suggest that AEs caused by intubation or cannulation can be avoided if there is a means of non-invasive delivery, i.e. aerosolized surfactant delivered through nasal continuous positive airway pressure (nCPAP) [5].

Current therapies for RDS in preterm infants are associated with the following challenges:

- Endotracheal intubation of preterm infants is an invasive procedure associated with airway tissue trauma, vagal stimulation, hypoxia, and bradycardia [1,2,3]. Additionally, insertion of small catheters into the infant trachea and positioning above the bifurcation can be traumatic. Both techniques require specialized skills, medical support, and training that must be kept current via frequent practice.
- Liquid bolus surfactant instillation via ETT is associated with airway obstruction (due to the large volume of liquid relative to preterm infant lung volumes) and transient physiological events such as hypoventilation, hyperventilation, changes in systemic blood pressure, alterations of cerebral blood flow, and other pulmonary and neurological effects.
- Respiratory support with nCPAP alone, albeit less traumatic compared to intubation/mechanical ventilation, results in delayed delivery of surfactant or absence of exogenous surfactant administration. This can lead to:
 - Atelectasis
 - Stress within the lungs associated with pneumothoraces and bronchopulmonary dysplasia (BPD)

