Infants receiving active drug will continue on nCPAP/nIMV after dose completion. If oxygenation and ventilation requirements increase within 96 hours after birth, AeroFact administration may be repeated up to three times for a total of 4 doses over the first 96 hours after birth. Re-dosing of AeroFact (same randomized group) will be allowed if the RSS to maintain SpO₂ between 90 and 95% is 1.5 to 2.39 and at least two hours have elapsed since the start of the previous dose:

- If FiO₂ > 0.23, re-dosing will occur.
- If FiO₂ ≤ 0.23, re-dosing is at the discretion of the investigator.

SpO₂ between 90-95% must be used to meet study eligibility through 96 hours for all study groups (Active/Control). Site-specific SpO₂ clinical guidelines may be used after 96 hours. Each site must use these guidelines uniformly across treatment groups. All infants randomized will be clinically managed until the criteria for treatment escalation have been met. If at any time the criteria for treatment escalation are met in any of the three treatment arms, intubation and/or bolus instillation of surfactant may be administered per site's standard of care. Oxygenation, ventilation parameters, nasal congestion/aspiration and dosing tolerance will be collected for each bolus instillation of surfactant.

Criteria for treatment escalation for AeroFact or nCPAP/nIMV only therapy includes any of the following:

1. Respiratory Symptom Severity (RSS) ≥ 2.4
2. Partial Pressure of Carbon Dioxide (PCO₂) > 65 mg Hg and/or pH < 7.20
3. Base deficit > 10 mEq/L, on two blood gases 4 hours apart
4. nCPAP > 8 cm
5. Three severe apneas with bradycardia within six hours requiring escalation of support
6. Infant's work of breathing has increased warranting escalating therapy, but infant does not meet RSS or other criteria above.

Data on all enrolled infants will be assessed through 40 weeks PMA or discharge from the NICU. Information to include: maternal/infant delivery, resuscitation history, oxygenation/ventilation parameters, concomitant medications of interest, and safety. Oxygenation and ventilation mode/parameters routinely monitored q 8 hours through Day 7, daily days 8 through 28, and daily at weeks 35 to 37 and 39 to 40 PMA/discharge. If an infant is discharged from the NICU prior to 36 and/or 40 weeks, a study member will call the family to verify the respiratory support status.

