12.3 Sample Size Determination and Rationale

[figure not shown]
Two hundred and sixty-one (261) subjects (87 in each arm) will be randomized in a 1:1:1 ratio in order to assure that 246 subjects (82 in each arm) complete the study. The randomization will be stratified by site, gestational age and dosing group.

Infants requiring treatment escalation in the AeroFact dose groups is estimated to be 20% and in the control group is estimated to be 40%, with an odds ratio of 0.375.

Under the above assumptions, 82 subjects in each treatment group will be required, to meet the Type I error rate of 0.05 and 80% statistical power. To accommodate the potential dropouts, a 5% dropout rate is included in this sample size calculation.

The sample size is depicted in Figure 12.1.

Figure 12-1: Sample Size

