12.4 Randomization

Infants will be block randomized in a 1:1:1 partially-blind fashion to receive one of two doses of AeroFact (Active) or Control. The randomization will be stratified by site and gestational age. There will be two sets of randomization envelopes, one for each gestational age group and they will be color-coded. If twins or triplets are enrolled, only the first sibling will be randomized and subsequent siblings will receive the same treatment assignment.

Treatment group will be randomly assigned using a predetermined randomization schedule created by an independent individual who is not on the study team. The randomization schedule will be generated using an appropriate block size to help maintain treatment groups of equal size within each age strata. Subjects who do not complete the study will not be replaced.

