12.12 Statistical Methods

A Statistical Analysis Plan (SAP) will be developed and approved before the database is locked. The SAP will present the detailed statistical methodology to be used in analyzing the efficacy and safety data from this trial. All inferential statistical analysis will be based on a two-sided test with a Type I error rate of 0.05.

All the efficacy analyses presented here will be conducted using both ITT and PP populations. All safety analyses will be conducted using the Safety population. All data collected will be summarized according to the variable type.

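### For bolus surfactant, the structured oxygenation and tolerance records start at instillation, so brief events during the preceding intubation or cannulation depend on discretionary AE reporting, and the gap is unequal between arms

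*Combined protocol and SAP*

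**What the plan says.** Section 8.1.4 sets the tolerance times for both routes: "Tolerance of surfactant dosing by AeroFact or bolus instillation will be assessed at 4 hours and 24 hours after the start of administration". Table 1 footnote 10 makes the bolus starting point explicit, counting from the instillation. Section 12.2.4 covers the period during each dose or instillation and up to 24 hours after it, and adds that any new dose of either kind closes the running window and opens another.

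For oxygenation and respiratory parameters, Table 1 footnote 6 asks for a reading before AeroFact dosing and then every 15 minutes from the start of the dose. For a bolus it says only: "These parameters will be collected after the start of AeroFact administration or bolus instillation of surfactant for all groups". The synopsis (Study Design) likewise places the bolus records after each instillation.

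Nasal congestion is handled differently. Footnote 9 and Section 8.1.3 have it assessed before and during a bolus as well as an AeroFact dose.

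On escalation, Section 4.1 says "intubation and/or bolus instillation of surfactant may be administered", so an infant may be intubated without receiving a bolus. No section starts an oxygenation or tolerance record at laryngoscopy, intubation or cannulation.

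**The concern.** Section 2.1 gives the reason for developing the product: "Endotracheal intubation of preterm infants is an invasive procedure associated with airway tissue trauma, vagal stimulation, hypoxia, and bradycardia". It lists the effects of liquid instillation separately. The structured records follow the instillation, whereas the harms just quoted belong to the step before it.

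Safety and tolerability is a secondary objective (Section 3.1.2), and Sections 8 and 12.2.4 name oxygenation and bradycardia as safety measures. The general AE route does not fill the gap reliably. The list of AEs of interest in Section 8.2.1.1 contains no desaturation, bradycardia or intubation injury, so such an event must be judged significant by the investigator (Section 8.2.1.2). Section 2.2.7.1 itself describes falls in saturation and heart rate with tube or cannula delivery as usually short-lived. The routine 8-hourly readings in Section 10.1.5.1 are too sparse to catch them.

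At stake is the descriptive tolerability comparison of AeroFact with control. If control infants undergo the airway procedure more often, and its brief harms are recorded less completely there, the summary understates the control burden.

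**Working it through.** **1. The plan's own figure.** Section 12.3 states "Infants requiring treatment escalation in the AeroFact dose groups is estimated to be 20% and in the control group is estimated to be 40" per cent, and "82 subjects in each treatment group will be required, to meet the Type I error rate of 0.05 and 80% statistical power". Section 12.12 makes the tests two-sided. With pooled variance and no continuity correction:

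n = [1.96 × √(2 × 0.30 × 0.70) + 0.8416 × √(0.40 × 0.60 + 0.20 × 0.80)]² / (0.40 − 0.20)² = (1.270 + 0.532)² / 0.04 ≈ 81.2, so 82 per arm.

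With 5% dropout, 82 / 0.95 = 86.3, so 87 per arm and 3 × 87 = 261. The plan's figures reproduce, and 87 per arm is used below.

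**2. The records side by side.**

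| Record | AeroFact dose | Bolus surfactant |
|---|---|---|
| Oxygenation and respiratory (footnote 6, synopsis) | Reading before the dose, then every 15 minutes from its start | After the start of instillation; no earlier reading stated |
| Tolerance (8.1.4, footnote 10, 12.2.4) | 4 h and 24 h from start of dose | 4 h and 24 h from start of instillation |
| Nasal congestion (footnote 9, 8.1.3) | Before and during | Before and during |
| AEs and SAEs (8.2.1.2, 8.2.1.3, 8.2.6.1) | From randomization | From randomization |
| Intubation without a bolus (4.1) | No record of its own | No record of its own |

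**3. Why the gap is unequal.** A control infant has had no surfactant before the first bolus, so no tolerance window is open at the airway procedure. An AeroFact infant intubated within 24 hours of a dose still has that dose's window open (Section 12.2.4). A procedural event may then be recorded, as a tolerance event of AeroFact.

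**4. Infants affected, at the planning rates.**
- Control: 87 × 0.40 = 34.8, an upper figure because escalation need not lead to a procedure.
- Each AeroFact arm: 87 × 0.20 = 17.4, an upper figure for the same reason and because some infants are inside an open window.

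**5. Lost incidence.** Let p be the share of infants with the procedure who have an event confined to the time before instillation. The documents give no value for p. Assume nothing is captured in control.
- Lost in control: 0.40p.
- Lost in an AeroFact arm: between 0 (all captured by open windows) and 0.20p (none captured).
- Understatement of the difference: from 0.40p − 0.20p = 0.20p to 0.40p − 0 = 0.40p.

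| p (assumed) | Understatement, percentage points |
|---|---|
| 10% | 2 to 4 |
| 30% | 6 to 12 |
| 50% | 10 to 20 |

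**6. Sensitivity to the rates.** Section 2.2.3.2 reports instilled surfactant in 45% of historical controls and 25% of AeroFact infants in Part II of the Phase 2a study. The ratio is then 0.45 / 0.25 = 1.8 instead of 2.0. The understatement runs from 0.45p − 0.25p = 0.20p to 0.45p.

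**The case against.** The strongest reply is that nothing is truly lost. AEs and SAEs are collected from randomization, clinically obtained blood gases are recorded before intubation (Table 1 footnote 2), and nasal congestion is assessed before a bolus. This stands. A reader might infer that procedural harm goes unrecorded altogether; the documents do not support that. What lacks a structured record is the brief event that the investigator does not judge significant.

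Second, Section 8.1.4 does not define the start of administration for a bolus, and the items on the tolerance form are not in the documents. A 4-hour form that looks back to the procedure cannot be excluded. This also stands, but footnote 10 counts from instillation and nothing in the protocol requires a look-back.

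Third, the rule is nominally the same for both routes, and the switch to the AeroFact interface also comes before the dose starts (Section 4.1). That is fair, and the fix should cover both. The asymmetry remains in the prior oxygenation reading and in the open window.

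Fourth, the size is partly constructed. The 40% and 20% describe escalation, not procedures. An infant may have more than one procedure, p is assumed, and events that continue into instillation are already covered. Section 12 describes no inferential between-arm test of tolerability, and tolerance is assessed per dose. All of this stands, so the figures are an illustration and not an estimate of bias in a planned test.

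Finally, intubation or cannulation with bolus is itself the primary endpoint. That counts the procedures but does not describe their harms.

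**Conclusion.** The point holds in limited form. Structured oxygenation and tolerance recording for a bolus begins at instillation, so brief desaturation or bradycardia during the preceding airway procedure is left to discretionary AE reporting. Control infants are the less well covered.

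At the planning rates this concerns up to about 35 control infants and at most about 17 in each AeroFact arm. The between-arm difference is understated by roughly 0.20p to 0.40p, against AeroFact. That range rests on the planning escalation rates, an assumed p, and no capture in control; any control event reported as an AE reduces it. A reader might infer that events are missed exactly twice as often in control. The documents do not support that either, because the ratio of two belongs to assumed escalation rates and ignores the open AeroFact windows.

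The primary endpoint and the sample size are unaffected. So is the expected comparison of the two doses, since the plan assumes the same rate in both AeroFact arms. This is an inexpensive improvement to safety data collection and not a threat to the trial's main result.

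**What to change.** In Section 8.1.4, Table 1 footnotes 6 and 10, and Section 10.1.5.1:
- Define the start of the record as the first laryngoscopy or cannulation attempt for a bolus, and as the switch to the AeroFact interface for an AeroFact dose.
- Take one oxygenation reading before the procedure in both cases.
- Keep the existing 15-minute, 4 h and 24 h points.
- Complete the same record for an intubation without a bolus.
- Summarise procedural desaturation and bradycardia descriptively, per infant, by randomized arm.

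The change is to wording and the case report form, uses bedside monitoring already in place, and alters no treatment decision. At the planning rates it involves about 34.8 + 17.4 + 17.4 = 69.6, or 70, infants, counting one procedure each; repeat procedures and intubations without a bolus add to this. The downside is a slightly longer form, some of it completed just after urgent procedures by staff who know Active from Control (Section 10.1.3.1). Values should therefore be taken from the bedside monitor where possible.

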8.1.5 Clinical Blood Gas Measurements

Blood gas measurements drawn for clinical care only will be recorded if collected prior to dosing, and/or as verification for meeting escalation criteria or in relationship to an SAE.

Supplemental oxygen and respiratory support will be adjusted to maintain SpO₂ between 90% and 95% during the first 96 hours after birth.

8.2 Adverse Events/Co-Morbidities of Prematurity

Occurrence of any AEs of interest (Co-morbidities of prematurity) will be collected and recorded until discharge or 40 weeks PMA. Only SAEs that result in an outcome of death will be recorded during Part II. Death is not an SAE but the outcome of the SAE.

8.2.1 Definitions

8.2.1.1 Co-Morbidities of Prematurity (AEs of interest) include:

- Culture Proven Sepsis
- Cystic Periventricular Leukomalacia (PVL)
- Hearing Loss
- Hydrocephalus requiring shunt
- Intraventricular Hemorrhage (IVH) Grades 1, 2, 3, or 4 (Worst Grade)
- Isolated Gastrointestinal Perforation without NEC
- Necrotizing Enterocolitis (NEC) requiring treatment
- Patent Ductus Arteriosus (PDA) requiring ligation
- PDA requiring treatment with indomethacin, ibuprofen, or acetaminophen
- Pneumothorax requiring chest tube
- Pulmonary Hypertension
- Pulmonary Interstitial Emphysema (PIE)
- Retinopathy of Prematurity (ROP) Stages 1, 2, 3, 4, or 5 (Worst Grade)
- Severe hypotension
- Severe pulmonary hemorrhage
- Tracheal Stenosis
- Tracheomalacia
- Vocal Cord Paralysis

BPD is not recorded as an AE but is recorded as an outcome at 36 and 40 weeks PMA.

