2.2.3 Summary of Clinical Results

2.2.3.1 APC-AF-CLN-001-Safety Analysis Conclusions:

- The overall incidence of TEAEs was low among AeroFact patients; 3 patients (30%) had 1 or more TEAE(s) in Part I, and 5 patients (23.8%) had 1 or more TEAE(s) in Part II.
- There were no TEAEs which were assessed by the Investigator as related to the study drug, device, or procedure, and none led to premature discontinuation from the study drug or premature discontinuation from the study.
- The most common TEAEs reported were patent ductus arteriosus occurring for 1 patient (10%) in Part 1 and for 3 patients (9.5%) in Part II, and pneumothorax occurring for 1 patient (10%) in Part 1 and 1 patient (4.8%) in Part II.
- All TEAEs in Part I were mild and the majority of TEAEs in Part II were mild with a severe TEAE occurring in 1 patient (4.8%) (pulmonary hemorrhage identified after intubation).
- During Day 1 to study Day 4, following AeroFact dosing, there was 1 occurrence (10%) of moderate nasal congestion in Part I, and 5 occurrences (23.8%) of moderate nasal congestion and 1 occurrence (4.8%) of severe nasal congestion in Part II of the study. Nasal aspiration occurred in 2 patients (9.5%) in Part II on Day 1 in the study. Neither nasal congestion or nasal aspiration data were available from the historical control patients for comparison.
- One patient in Part I and 1 patient in Part II of the study had an SAE. Both patients had the SAE of culture-proven sepsis, which was not related to the study drug, the device, or the procedure, did not emerge during the treatment period, and resulted in death.
- Generally, the incidence of AEs associated with dosing tolerance in the first 24 hours was low; the incidence of AEs for AeroFact only vs. AeroFact plus bolus surfactant demonstrated comparability.
- The incidence of post-dose comorbidities of prematurity and AEs was low and consistent between the patients treated with AeroFact vs. historical controls.

2.2.3.2 APC-AF-CLN-001-Efficacy Analysis Conclusions:

- At 36 Weeks PMA, a larger proportion of patients receiving AeroFact in Part I and Part II of the study survived without BPD (88.9% and 78.9%, respectively) compared with Part I and Part II historical control patients (73.3% and 66.7%, respectively).
- The median (range) length of stay in the NICU for AeroFact patients in Part I and Part II was comparable to historical control patients.

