2.2.7 Risk Assessment

2.2.7.1 Risks to Subjects

The Sponsor has conducted risk analysis and the following clinical harms with overall high unmitigated risk have been identified:

- Hypoventilation, bradypnea, hypoxemia
- Progression of RDS (in the event of under-dosing)
- Skin irritation
- Pneumothorax, volutrauma

These clinical risks will be properly controlled and/or mitigated relative to the device design e.g. implementation of alarms, verification testing or labeling (instructions, warnings and cautions) prior to clinical trials on infants.

Furthermore, the drug delivery system will be tested for its safety following ISO and IEC standards for materials, biological and electrical safety, and electromagnetic compatibility.

The toxicology program in two species of newborn animals did not identify any risks with the dose or the route of administration.

The most common side effects reported when premature infants are given surfactant through the ETT or cannula are:

- decreases in oxygen saturation (SpO₂)
- plugging of breathing tube
- decreases in heart rate, reflux of surfactant into the breathing tube
- the need for extra mechanical breaths to be given from the breathing machine

These events are generally brief and not associated with serious complications or death.

Risks of aerosolized surfactant are unknown. However, due to the small aerosol size and gradual nature of the liquid aerosol administration, they are expected to be less than those associated with administration through an ETT/or cannula. The surfactant will be given by skilled caregivers in the NICU who can respond to all of these potential side effects should they occur. Risks of using the AeroFact drug delivery system are detailed in the Investigator's Brochure.

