Co-morbidities of prematurity (e.g.: pneumothorax, IVH, PDA, NEC, sepsis, etc.) and adverse events (treatment-related or otherwise) will be collected to 40 weeks PMA/Discharge.

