8.2.1.2 Adverse events

Adverse events (AE) for this study include the co-morbidities of prematurity listed above or any untoward medical occurrence deemed significant by the Principal Investigator. An AE does not necessarily have to have a causal relationship with this treatment. An AE may also occur which may be related to the medical device that is being tested. The Investigator will be asked to determine the causal relationship of each AE to the investigational device. This includes any event that is the result of incomplete user manual information or of incorrect use of the medical device.

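### Pneumothorax is captured systematically only when it needs a chest tube; lesser cases depend on an investigator who knows Active from Control, and the pulmonary hemorrhage wording needs reconciling

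*Combined protocol and SAP*

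**What the plan says.** **Risk analysis (Section 2.2.7.1).** The sponsor lists harms with high unmitigated risk. They include pneumothorax with volutrauma, with no severity qualifier, and "Hypoventilation, bradypnea, hypoxemia".

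**General collection statement (Section 4.1).** "Co-morbidities of prematurity (e.g.: pneumothorax, IVH, PDA, NEC, sepsis, etc" and other adverse events are to be collected to 40 weeks PMA or discharge. Pneumothorax again carries no qualifier.

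**Operative list (Section 8.2.1.1).** The items are "Pneumothorax requiring chest tube" and "Severe pulmonary hemorrhage". The same list takes IVH at grades 1 to 4, ROP at stages 1 to 5, and pulmonary interstitial emphysema without any qualifier.

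**AE definition (Section 8.2.1.2).** An AE is a listed co-morbidity or "any untoward medical occurrence deemed significant by the Principal Investigator".

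**Discontinuation (Section 5.4).** Study treatment stops for a pneumothorax requiring a chest tube, or for pulmonary hemorrhage described as frank bleeding from the lungs not related to suctioning irritation or infection.

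**Dosing-period record (Table 1 footnote 6; Section 10.1.4.1).** Every 15 minutes, staff record FiO2, SpO2, PEEP/CPAP, flow, mean airway pressure and support status, together with nasal congestion and suctioning. Heart rate and respiratory rate are not in the list. Dosing-tolerance events are assessed at 4 and 24 hours, but the items are not given. Sections 8 and 12.2.4 say that safety is assessed through monitoring of, among other things, bradycardia.

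**The concern.** A harm that the sponsor's own risk analysis singles out is captured systematically only above a treatment threshold. Below it, capture depends on a judgement of significance made separately at about 45 sites (Section 5) by investigators who know whether the infant received AeroFact. Discretionary, unmasked ascertainment can bias the active-control comparison in either direction: an investigator may look harder for an air leak after aerosol dosing, or may be readier to call a small one insignificant. Whether a chest tube is placed is itself a clinical decision taken with the same knowledge.

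This trial is meant to choose the dose and dosing strategy for Phase 3 (Section 4.1), so its comparative safety tables will carry weight.

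The hemorrhage wording is a separate matter. The AE list and the discontinuation rule use different terms, and the term in the list is not defined. Sites cannot tell from the text whether the two describe the same event.

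**Working it through.** No design figure depends on this point, so there is none to reproduce. The check is a comparison of sections, with simple arithmetic on the phase 2a counts.

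**1. Sections compared on each harm**

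| Harm | Risk analysis (2.2.7.1) | General collection (4.1) | AE list (8.2.1.1) | Stops treatment (5.4) |
|---|---|---|---|---|
| Pneumothorax | Named, unqualified | Named, unqualified | Only with chest tube | Only with chest tube |
| Pulmonary hemorrhage | Not named | Not named | Only if severe (undefined) | Frank bleeding |
| Bradypnea, hypoventilation | Named | – | Not listed | – |
| Hypoxemia | Named | – | Not listed, but SpO2 is recorded every 15 minutes | – |

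For pneumothorax, Sections 2.2.7.1 and 4.1 are wider than Section 8.2.1.1. For hemorrhage, Sections 5.4 and 8.2.1.1 use different words.

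**2. Who decides below the threshold, and what that person knows**

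Section 8.2.1.2 leaves unlisted events to the Principal Investigator. Section 10.1.3.1 (step 1) opens Active or Control to study staff, and the SAE report asks the site for that group (Section 8.2.7). Sections 6.6 and 12.6 mask dose level only. One sentence in Section 4.1 could be read as masking AeroFact allocation altogether, but the next paragraph limits the masking to Active dose, and Control infants simply continue nCPAP or nIMV. The judgement is therefore unmasked for active versus control and masked for dose versus dose.

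**3. Phase 2a counts (Section 2.2.3.1)**

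The protocol reports "pneumothorax occurring for 1 patient (10%) in Part 1 and 1 patient (4.8%) in Part II". With 10 infants in Part I and 21 in Part II:

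- 1/10 = 10.0% and 1/21 = 4.8%, as stated.
- Pooled: (1 + 1)/(10 + 21) = 2/31 = 6.5%, Clopper-Pearson 95% CI 0.8% to 21.4%.

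The same section says "All TEAEs in Part I were mild", so the Part I pneumothorax was graded mild. In this protocol mild means that no special treatment is required (Section 8.2.2). If phase 2a used the same scale, that case might not meet the chest-tube term. Neither case is described as having or lacking a chest tube.

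**4. Illustration, by assumption only**

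The documents do not give the chest-tube share. Assume that any pneumothorax occurs in 5% to 10% of infants, close to the two phase 2a rates, and that 25% to 75% of cases need a chest tube. Per arm of 87:

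- any pneumothorax: 87 × 0.05 = 4.4 to 87 × 0.10 = 8.7;
- listed term: 87 × 0.05 × 0.25 = 1.1 to 87 × 0.10 × 0.75 = 6.5.

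The difference is what would depend on the investigator's judgement. It is not a count of events lost.

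**5. Dosing-period record**

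Sections 8 and 12.2.4 promise bradycardia monitoring and Section 2.2.7.1 names bradypnea, but the 15-minute list holds neither rate. Blood gases are recorded only if drawn for clinical care, and then before dosing, to verify escalation or in relation to an SAE (Section 8.1.5). The dosing-tolerance assessment might fill the gap; its items are not in the documents.

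**The case against.** The strongest reply is that nothing is excluded. Section 8.2.1.2 admits any event that the investigator finds significant, Section 4.1 names pneumothorax without a limit, and Section 8.2.1.3 requires all AEs to be documented on the CRF. This stands against any claim that lesser cases are shut out or that under-recording has been shown. It does not make capture systematic, because the duty to document begins only once an event counts as an AE.

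A reader might infer several stronger points that the documents do not support:

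- *The dose-dose comparison also rests on an unmasked judgement.* It does not; the investigator is masked to dose.
- *Pulmonary hemorrhage is one of the named high-risk harms.* It is absent from Section 2.2.7.1. Its case rests only on the differing words in Sections 5.4 and 8.2.1.1, and severe may have been meant as frank bleeding. An event that stops dosing would also probably be judged significant.
- *About half of pneumothoraces would be missed.* That extrapolates from one mild case in two, with an assumed grading scale and no chest-tube information.
- *All the named respiratory harms go unmeasured.* SpO2 covers hypoxemia, and marked hypoventilation can surface through the PCO2, pH and apnea escalation criteria in Section 4.1.
- *Phase 2a showed a pneumothorax signal.* No TEAE there was judged related to drug, device or procedure, and co-morbidities were described as consistent with historical controls.

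The risk list is also of unmitigated risks, which the sponsor says will be controlled through alarms, testing and labeling. That lowers the expected frequency but is no reason to capture the harm less completely. Skin irritation is on the list with no scheduled assessment, but a skin score would be an extra procedure rather than a repair of inconsistent text, and is not requested.

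**Conclusion.** The point holds as a limited but real weakness in safety ascertainment. Capture of pneumothorax is systematic only for chest-tube cases, which is narrower than Sections 2.2.7.1 and 4.1 imply. The remainder rests on a discretionary judgement made with knowledge of Active versus Control, so the active-control comparison is open to ascertainment bias of unknown direction and size.

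The phase 2a rate of 6.5% (0.8% to 21.4%) shows that the event is not negligible in this population, but it cannot fix how many cases would fall below the threshold. The remark about the mild Part I case assumes that phase 2a used this protocol's grading.

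The hemorrhage wording in Sections 5.4 and 8.2.1.1 must be reconciled. The missing heart rate and respiratory rate are minor, and conditional on what the dosing-tolerance form holds. The change is worth making because it is cheap, and the list already records IVH and ROP at every grade.

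**What to change.** 1. In Section 8.2.1.1 and on the AE CRF, replace the two items with *Pneumothorax, any* and *Pulmonary hemorrhage, any*. Give pneumothorax a treatment-given field (for example none, needle, chest tube) and hemorrhage a severity field with its terms defined, so that the chest-tube and severe subsets can still be tabulated.
2. Align Section 4.1 with the revised list, and state how the hemorrhage term in Section 8.2.1.1 relates to the one in Section 5.4. Leave the discontinuation criteria untouched.
3. List the dosing-tolerance items. Unless they already capture bradycardia and bradypnea, add heart rate and respiratory rate to the 15-minute record in Table 1 footnote 6 and Section 10.1.4.1.

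The cost is protocol and CRF wording, slightly more data entry, and a higher reported AE count, which the chest-tube and severe subsets will put in context. The CRF is not among the documents, so the extra entry cannot be sized exactly.
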